**6. Introduction****6.1 Background Information**

Stress is a well-established factor in the onset and persistence of burnout, anxiety, mood, and psychotic disorders. Sleep disorders further predispose individuals to, and exacerbate, these psychiatric symptoms. Individuals with mental health problems tend to have higher (social) stress reactivity and impaired stress recovery, which is compounded by sleep disturbances and sleep deprivation.

Relaxation can reduce stress, thereby potentially improving mental health symptoms. Moreover, stress-reducing interventions may enhance quality of life, social functioning, and occupational performance. While current stress-reducing interventions appear effective, they often require mental effort—such as focus and concentration—which may be compromised in patients.

To bridge this gap, a new e-Health application called **VRelax** has been developed. VRelax is a virtual reality self-management tool designed to reduce stress. It requires significantly less effort than traditional relaxation exercises due to its immersive qualities and has an immediate effect on perceived stress and emotional mental states.

Following a comprehensive literature review on the potential applications of Virtual Reality (VR) in forensic psychiatric populations—published in November 2021 in the *Tijdschrift voor Psychiatrie*—this study will be the first to assess the effects of VR-based relaxation in such a setting. The study aims to determine whether VR relaxation provides added value for both patients and staff, and how best to implement this technology within the hospital's operations.

Given that VR environments can simulate highly realistic situations that forensic psychiatric patients would otherwise be unable to experience due to their restricted freedoms, VR offers a powerful tool that addresses the limitations of confinement. The highly immersive nature of the application also benefits patients who are unable to engage in traditional relaxation exercises due to limited imagination or empathy skills.

This study will investigate the short- and medium-term effects of VRelax on both acute and chronic stress and compare these effects to a standard relaxation exercise of the participant's choice (Treatment As Usual, TAU). The study is based on previous work by Veling et al. (2021), in which the same VRelax application was tested in an outpatient setting.

---

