## Hypothesis of the Clinical Investigation

1. VRelax will reduce acute stress: the PRE-VAS score will be higher than the POST-VAS score.
2. VR relaxation will have a greater relaxing effect than standard relaxation: VAS scores and biomarkers will reflect a stronger relaxation effect.
3. VRelax will also reduce chronic stress through a cumulative effect, meaning the post-intervention PSS score will be lower than the pre-intervention PSS score.
4. There will be a difference in the acute effect over time; in other words, as the number of sessions increases, habituation or boredom may occur for both standard and VR relaxation. This will be measured by a decreasing difference between pre- and post-VAS scores per individual over time.

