## **13. Methodology**

### **13.1 Study-Specific Procedures**

The study consists of two blocks of 10 sessions: one block with VR and one without. Each participant thus serves as their own control.

The control sessions take place in the VR room, seated, with a total duration of 30 minutes (including 20 minutes of relaxation of their choice, e.g., reading, listening to music, watching a short film, body scan, etc.). The selected relaxation method is recorded for each session.

The VR sessions also take place in the VR room, seated, with a duration of 30 minutes (including 20 minutes of VRRelax with one or more 360° videos of the participant's choice). Guided meditation sessions are excluded, as they require the eyes to be closed. The selected videos are recorded per session.

Before and after each session, stress is assessed using VAS scores for stress/tension and happiness. At the beginning and end of each 10-session block, general stress levels are measured using the Perceived Stress Scale (PSS). After the final session of each block, a structured qualitative interview is conducted regarding the user experience. All groups receive the same pre- and post-intervention assessments.

During each relaxation session, physiological parameters are also measured using the Embrace Plus device ([www.Empatica.com](http://www.Empatica.com)), including heart rate, heart rate variability (HRV), respiratory rate, skin conductance, and skin temperature.

---

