**1 - (VAS score before / VAS score after)**

Descriptive statistics (mean, standard deviation, minimum, and maximum) will be computed for demographic, clinical, and outcome variables.

VAS scores for relaxation and happiness, as well as physiological parameters (heart rate, HRV, skin conductance, respiration), will be compared using **paired t-tests** between pre- and post-session time points.

Perceived Stress Scale (PSS) scores will also be compared between pre- and post-therapy blocks (each block consisting of 10 sessions) using a paired t-test.

To estimate the difference in effect between the VR treatment and standard relaxation, a **mixed model multilevel regression analysis** will be used. The model will include:

- Time (before vs after)
- Treatment (VR vs standard)
- Group (1 vs 2)
- Interaction term: Time × Treatment  
(with random intercept for “participant”)

The **interaction between time and treatment** is the primary parameter of interest.

Finally, **carry-over effects** will be examined by comparing VAS scores and physiological parameters between session 1, session 5, and session 10 using paired t-tests (S1 vs S5 and S5 vs S10).

---

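### Hypothesis 3 attributes a fall in PSS to VRelax, but the only analysis that names PSS is a before-after test within a block

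*Combined protocol and SAP*

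**What the plan says.** Hypothesis 3 (Hypothesis of the Clinical Investigation) reads: "VRelax will also reduce chronic stress through a cumulative effect, meaning the post-intervention PSS score will be lower than the pre-intervention PSS score". No comparator appears in it. Section 6.1 sets a wider aim: the study will investigate the "short- and medium-term effects of VRelax on both acute and chronic stress and compare these effects to a standard relaxation exercise".

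On design, section 13.1 states: "The study consists of two blocks of 10 sessions: one block with VR and one without". PSS is taken at the start and end of each block, so each participant who completes has a PSS change under both conditions.

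Section 16.2 gives PSS one sentence: "Perceived Stress Scale (PSS) scores will also be compared between pre- and post-therapy blocks (each block consisting of 10 sessions) using a paired t-test". It then introduces a mixed model "To estimate the difference in effect between the VR treatment and standard relaxation", with terms for time, treatment, group and Time × Treatment, the last being the parameter of interest. No outcome is named for this model. Hypothesis 2, which claims the advantage over standard relaxation, is to be judged thus: "VAS scores and biomarkers will reflect a stronger relaxation effect". PSS is not mentioned there. Nor is it among the primary or secondary endpoints in sections 8.1 and 8.2, which list the two VAS scores and the physiological parameters.

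**The concern.** Hypothesis 3 is a causal statement about VRelax. The paired t-test has a different null: that mean PSS does not change between the start and end of the block. Rejecting it shows that PSS moved, not why.

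Several influences act in both blocks. Participation lasts up to 4 months (13.4), other treatment is unrestricted (13.6), therapy schedules are rearranged for the study (13.3), and both conditions bring ten 30-minute seated sessions in the same room (13.1). A fall in PSS from any of these would meet the criterion in hypothesis 3. The standard block is the control for exactly such influences, and its PSS data are collected, but the PSS sentence in 16.2 does not use them as a control.

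At stake is the chronic-stress conclusion and the long-term part of the objective in 7.1. The acute VAS result is not.

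**Working it through.** **1. The plan's own figure.** The only sample size is 54, calculated for VAS (16.1). A two-sided paired t-test at alpha 0.05 with 80% power, difference 0.5, SDs 0.83 and 0.74 and an assumed correlation of 0 gives d = 0.5/√(0.83² + 0.74²) = 0.5/1.112 = 0.450, hence n = 41. Then 41 × 1.3 = 53.3, rounded up to 54. The figure is reproduced but does not concern PSS, for which the documents give no SD, target difference or expected drift.

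**2. Inputs for the check.** Completers: 54 × 0.7 = 37.8, taken as 38, with 54 as the upper case. Alpha is 0.05, two-sided (assumed; the plan does not state sidedness). The non-specific fall δ is expressed in SDs of the within-block PSS change. Its values are assumed, and the true VRelax effect is set to zero.

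**3. How often the planned t-test rejects.** The rejection probability is P(|T| > t₀.₉₇₅,ₙ₋₁), where T is noncentral t with n − 1 degrees of freedom and noncentrality δ√n (√38 = 6.164; √54 = 7.348).

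| Fall δ (SD) | δ√38 | Rejects, n = 38 | δ√54 | Rejects, n = 54 |
|---|---|---|---|---|
| 0 | 0 | 5% | 0 | 5% |
| 0.1 | 0.62 | 9% | 0.73 | 11% |
| 0.2 | 1.23 | 22% | 1.47 | 30% |
| 0.3 | 1.85 | 44% | 2.20 | 58% |
| 0.5 | 3.08 | 85% | 3.67 | 95% |

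**4. The controlled contrast.** For each participant take block-1 change minus block-2 change, and compare the VR-first and standard-first groups with a two-sample t-test. A shift common to a block has the same expectation in both groups and cancels; the group difference in means is twice the VR-minus-standard effect. In 20,000 simulated trials per setting (normal changes, equal group sizes, uncorrelated blocks, no VRelax effect, no carry-over) the contrast rejected in 4.6% to 5.2%. The settings were equal falls of 0, 0.2, 0.3 and 0.5 SD in both blocks, 0.6 SD in block 1 only, and 0.5 then 0.1 SD, each with n = 38 and n = 54. In the last two settings the VR-block t-test rejected in 40% and 42% of trials (n = 38), and in 55% and 56% (n = 54).

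**5. Price in precision.** With σ the SD of a block change, uncorrelated blocks and 38 completers:
- single-block change: SE = σ/√38 = 0.162σ
- VR minus standard: SE = σ√(2/38) = 0.229σ, a ratio of √2, about 1.4
- block-1 comparison between groups of 19: SE = σ√(2/19) = 0.324σ

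With correlation r between block changes and equal variances, the ratio for the contrast is √(2(1 − r)), so positive correlation reduces the loss.

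**The case against.** The strongest reply is that the controlled test is already in the plan. The Time × Treatment model follows directly after the PSS sentence, names no outcome and so excludes none, and fits PSS, which has before and after values in both blocks. Section 16.2 also assigns VAS to paired t-tests, yet VAS is plainly meant for the model too, and section 6.1 promises a comparison on chronic stress. This stands in part. A reader might infer that the trial has no controlled analysis of PSS at all; the documents do not support that. They leave it open: the model is not tied to PSS, hypothesis 2 names only VAS and biomarkers, and hypothesis 3 carries its own before-after criterion.

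Three further replies stand.
- The drift sizes are assumed. Nothing in the documents shows that a fall of 0.3 or 0.5 SD is likely, or that drift would be downward. Regression to the mean is a weak argument here, because the eligibility criteria (10.3, 10.4) set no stress threshold.
- A reader might infer that the investigators will set a significant VR block against a non-significant standard block and call that an advantage. No section plans this; 16.2 assigns the difference in effect to a model interaction.
- Hypothesis 3 does not claim superiority. Standard relaxation is an active comparator, so if both methods lower chronic stress equally the contrast is null although VRelax works. Redefining the hypothesis as superiority would change the question. The contrast is also exposed to carry-over: a cumulative effect is postulated and no washout is described, so VR-first participants may enter block 2 with altered PSS.

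None of this lets an uncontrolled before-after test support a causal statement.

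**Conclusion.** The concern holds in limited form. Followed as written, hypothesis 3 and the one analysis that names PSS would count a non-specific fall as an effect of VRelax, and the comparison on chronic stress promised in 6.1 is not assigned to any stated analysis. The rejection rates of 9% to 85% (38 completers, falls of 0.1 to 0.5 SD) illustrate the mechanism and do not predict what will happen in this trial. They rest on assumed drift, zero VRelax effect, two-sided testing and 38 completers; the figure of about 5% for the contrast also assumes no carry-over. Severity is minor to moderate: PSS is not a listed endpoint, and the primary VAS endpoint is unaffected.

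**What to change.** In section 16.2, name PSS as an outcome of the VR-versus-standard analysis: VR-block change minus standard-block change, with a block (period) term. If the before/after form of the mixed model is kept, that term must act on the change, that is, as block × time. Base any statement that attributes a PSS reduction to VRelax on this contrast. Keep the within-block PSS changes with 95% confidence intervals, reported as change over time and not as an effect of VRelax, and add a sentence to that effect beside hypothesis 3.

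State the limits with the result. The contrast measures benefit over standard relaxation, so finding no difference does not show that VRelax has no effect. Its SE is about 1.4 times that of a single-block change if the block changes are uncorrelated. Because no washout is described, carry-over may distort block 2; show the block-1 comparison between the two groups as a sensitivity check, accepting its lower precision.

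The cost is wording and analysis only. All the PSS measurements needed are already scheduled.

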## Synopsis of the clinical investigation

TITLE	The effects of relaxation using Virtual Reality, by forensic psychiatric patients. A randomized crossover clinical trial
ACRONYM	VRelax study
SPONSOR	UGent-UZGent
COORDINATING INVESTIGATOR	[name]. [name]
NAME OF DEVICE	
 
- PICO VR bril, de software is VRelax
 
- Embrace plus
 

MANUFACTURER	
 
- PICOXR.com
 
- Vrelax.com
 
- Empatica.com
 

STUDY DESIGN	Cross-over randomized controlled trial
CENTER(S) / COUNTRY(IES)	UZGent en PC Sint-Jan Baptist, in Zelzate, Belgium
OBJECTIVES	
Primary Objective  To determine whether VR relaxation has a significant effect on a person's stress level. This will be assessed, among other measures, through a change in the VAS relaxation score, where an average improvement of 0.5 out of 10 is considered clinically relevant. With this study, we aim to gain insight into the effects of VR relaxation on both subjective and objective stress, heart rate, and other physiological parameters.
 
Secondary Objectives  We will also examine changes in the VAS score for happiness, where an average improvement of 0.5 out of 10 is considered clinically relevant. We aim to assess whether VR relaxation has a greater relaxing effect compared to standard relaxation. Additionally, we want to gain insight into the feasibility of implementation and evaluate the user-friendliness of the application. Furthermore, we intend to identify the most suitable types of VR environments for relaxation and investigate whether the effect may be greater in patients with intellectual disabilities or other psychiatric disorders.

ENDPOINTS	
Primary Endpoint A change in the VAS score for relaxation, where an average improvement of 0.5 out of 10 is considered clinically relevant.
 
Secondary Endpoints A change in the VAS score for happiness, where an average improvement of 0.5 out of 10 is considered clinically relevant.

STUDY DURATION	3 years
NUMBER OF PATIENTS	54
INCLUSION CRITERIA	Be admitted for at least 4 months as a forensic psychiatric patient within medium or high security, at Sint-Jan Baptist in Zelzate.

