### Sub-hypotheses:

1. The difference in effect between standard and VR relaxation will be greater in patients with intellectual disabilities, as they have a less developed capacity for imagination.

2. There are differences in video preferences among patients with different psychiatric disorders. For example, individuals with autism may prefer static videos, while those with borderline personality disorder may prefer interactive videos.
3. The relaxing effect will manifest more quickly when using VR than with standard relaxation.

---

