## **7. Objective of the Clinical Investigation**

### **7.1 Primary Objectives**

The main objective is to examine the relaxing effect of VRelax. We aim to measure the magnitude and duration of the effect and assess the difference compared to standard relaxation exercises. What is the immediate effect, and what is the long-term impact? Is there any habituation? Which physiological parameters are most influenced?

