## **9. Design of the Clinical Investigation**

The study design is a crossover randomized controlled trial. In this way, each participant serves as their own control, which helps eliminate individual/genetic effects on the measurements. Since this study involves a heterogeneous patient population with varying diagnoses and comorbidities, this design helps limit variability to obtain statistically significant results with a feasible sample size. It also minimizes the influence of external factors on the study outcomes.

The study protocol was extensively tested among volunteer staff members at Sint-Jan Baptist to identify and resolve potential errors or problems before the official start of the trial, ensuring a relevant and high-quality protocol.

This is also the first clinical study to test the VRelax app in a forensic psychiatric inpatient population, while also incorporating physiological parameters.

---

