## **10. Population**

### **10.1 Number of Subjects**

The primary endpoint selected is a change in the VAS relaxation score, where an average improvement of 0.5 out of 10 is considered clinically relevant between pre- and post-session time points.

The standard deviations used (0.83 for standard relaxation and 0.74 for VRelax) were estimated based on the results of a comparable study in an outpatient population, as described in the article by Veling et al. (2021).

The chosen statistical power is 80%, and the type I error rate was set at 0.05.

An expected dropout rate of 30% was included.

Calculations were performed using the GPower software.

The calculated required sample size for detecting a difference in VAS relaxation scores is **54**.

All participants are forensic psychiatric patients admitted to PC Sint-Jan Baptist in Zelzate and expected to remain there for at least 4 more months, ensuring their availability throughout the entire study period.

---

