### **13.5 Randomisation**

As soon as all participants are confirmed, randomisation will be carried out using SAS software to assign them to one of the two groups.

---

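### If all sessions enter the VR-versus-standard model, a participant random intercept alone does not secure a valid standard error, and omitting Time × Block can bias the comparison when sequence groups are unequal

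*Combined protocol and SAP*

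**What the plan says.** Section 16.2 estimates the difference between VR and standard relaxation with a multilevel regression. Its fixed effects are Time (before, after), Treatment, Group and Time × Treatment. The only random effect is given as "with random intercept for “participant". There is no block, Time × Block or session term. The section names the interaction as its main parameter.

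Section 13.1 sets two blocks of ten sessions, with VAS taken before and after each, so 2 × 10 × 2 = 40 readings per patient. Section 16.2 speaks of changes around each session but does not say which sessions the model uses.

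Other text bears on whether the model fits:

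- **Variation in effect.** The sub-hypotheses state that "The difference in effect between standard and VR relaxation will be greater in patients with intellectual disabilities". The Synopsis plans to "investigate whether the effect may be greater in patients with intellectual disabilities or other psychiatric disorders". Section 9 says "this study involves a heterogeneous patient population with varying diagnoses and comorbidities".
- **Change over time.** Hypothesis 4 expects that "as the number of sessions increases, habituation or boredom may occur for both standard and VR relaxation".
- **Group sizes.** Section 13.5 says "randomisation will be carried out using SAS software to assign them to one of the two groups", with no ratio or blocking. Section 10.1 says "An expected dropout rate of 30% was included".
- **Status of the comparison.** Section 7.1 puts among the primary objectives to "assess the difference compared to standard relaxation exercises". The Synopsis lists the same comparison as secondary.

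**The concern.** A participant intercept alone treats any two readings of a patient as equally correlated, whether they come from the same session, the same block or different conditions. Two departures are plausible here and act in opposite directions.

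- If patients differ in how much more VR helps them than standard relaxation, ten sessions per block do not average that difference away. The model counts the sessions as nearly independent evidence, so its standard error is too small.
- If a patient's level differs from session to session, pre and post share that shift and it cancels in the change. The model leaves it in the residual, so its standard error is too large.

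The second issue is bias. If the pre-post change is smaller in block 2, and more patients start with one condition than with the other, the condition given first more often gains an advantage that the model credits to treatment.

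At stake are the p-value and confidence interval of the VR-versus-standard comparison, which Section 16.2 puts at the centre of this model.

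**Working it through.** **Inputs from the documents.** N = 54, 30% dropout, SDs 0.83 (standard) and 0.74 (VRelax), difference 0.5, power 80%, alpha 0.05 (Sections 10.1 and 16.1); ten sessions per block (Section 13.1).

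**The plan's own figure.** Taking the SDs as uncorrelated between conditions, the SD of the difference is √(0.83² + 0.74²) = √1.2365 = 1.112. A two-sided paired t-test then needs 41 patients (power 80.2%; 40 give 79.2%), and 41 × 1.3 = 53.3, rounded up to 54. So 54 is reproduced with zero correlation, which is also used below. Section 16.1 does not state the correlation, or whether the SDs describe single-session changes; both are assumptions here.

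**Assumed inputs.** Completers: 54 × 0.7 = 37.8, taken as 38. Effect SD (τ): the between-patient SD of the VR-standard difference. Session SD (s): the SD of a level shift shared by the pre and post readings of one session.

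**Standard error.** Let v = 1.2365 − τ² be the session-to-session part of the two change variances.

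- True variance of the estimate = (τ² + v/10)/38.
- Model variance = 4·s₂/(10 × 38), where the residual variance is s₂ ≈ v/4 + τ²/8 + s²·38/39. The τ²/8 term places the patient's extra effect in the post reading, half in each condition with opposite sign.

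| τ | s | s₂ | Model SE | True SE | Ratio | Type I error |
|---|---|---|---|---|---|---|
| 0.3 | 0 | 0.298 | 0.056 | 0.073 | 0.76 | 13% |
| 0.5 | 0 | 0.278 | 0.054 | 0.096 | 0.56 | 27% |
| 0.5 | 0.5 | 0.522 | 0.074 | 0.096 | 0.77 | 13% |
| 0.3 | 1.0 | 1.272 | 0.116 | 0.073 | 1.58 | 0.2% |

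For the first row, v = 1.1465. The true variance is (0.09 + 0.11465)/38 = 0.00539. The residual variance is 0.2866 + 0.0113 = 0.298, and √(4 × 0.298/380) = 0.056. Type I error is the normal two-sided tail beyond 1.96 × ratio.

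Simulation (3,000 to 4,000 trials per setting) agrees. Type I error by session SD:

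| Session SD | τ = 0.2 | τ = 0.3 | τ = 0.5 |
|---|---|---|---|
| 0 | 8% | 14% | 27% |
| 0.5 | 2% | 4% | 13% |
| 0.75 | 0.6% | 1.4% | 5.7% |
| 1.0 | 0.03% | 0.3% | 1.8% |

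The interval is affected even when VR truly differs from standard. At a true difference of 0.5 and session SD 0, coverage of the 95% interval is 86% (τ = 0.3) and 73% (τ = 0.5). On the conservative side (session SD 1.0, τ = 0.3), power for a difference of 0.2 is 36% against 77% with patient means. For 0.3 it is 84% against 98%, and for 0.5 about 100% for both. A period-adjusted t-test on patient means kept type I error at about 4 to 6% throughout.

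**Block.** Let the improvement over a session be δ higher in block 2 than in block 1 (δ negative if it shrinks), with n₁ patients starting on VR and n₂ on standard. The VR-minus-standard estimate is then off by δ(n₂ − n₁)/N.

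- δ = −0.25 at 22 versus 16: −0.25 × (−6)/38 = 0.039.
- δ = −0.5: 0.079.
- Equal groups: 0.

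A level shift that moves pre and post alike cancels: a simulated 1-point shift at 22 versus 16 moved Time × Treatment by −0.001. With δ = −0.25, fitted models gave a bias of 0.045 as planned, still 0.045 with a block main effect added, and 0.007 with Time × Block added (15 runs each, so only approximate).

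With no effect variation and a drop of 0.25, type I error is 11% at session SD 0, 2.3% at 0.5 and 0.5% at 0.75. The chance of a split at least as unequal as 22 versus 16 among 38 is 42% under simple randomisation. It is 13% if 27/27 is forced and 16 patients drop out at random.

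**The case against.** The strongest reply is that the large inflation figures sit at session SD 0, meaning that a patient's level never moves across 20 sessions. That is hard to believe in a group that Section 6.1 describes as stress-reactive. At session SD 0.5 only the largest effect SD shown inflates materially, and at 0.75 nothing in the table exceeds about 6%. This stands. A reader might infer that the planned p-value is too optimistic; the documents do not support that, because they give no variance components and the error may equally be conservative.

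A reader might also infer that leaving out a block main effect biases the comparison. It does not, because a level shift cancels in Time × Treatment. Bias needs unequal groups and a change that differs between blocks. Hypothesis 4 predicts habituation as sessions accumulate, but does not say that it persists when the patient switches condition. Section 13.5 randomises once all participants are confirmed, which is compatible with a fixed 27/27 list.

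Third, the Synopsis and Section 8.1 make the pre-post change the primary endpoint, and the harm lies below 0.5, the only threshold the protocol names. So it would be wrong to infer that the primary endpoint test is compromised. But Section 7.1 lists the comparison as a primary objective, and the size of the VR advantage bears on the investment question in Section 7.2.

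Finally, if only one pre/post pair per block enters, inflation nearly vanishes: 5.2 to 5.9% at session SD 0 and under 2% at 0.5 or more. The standard-error point is therefore conditional on all sessions being used.

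**Conclusion.** The point holds in conditional form and should be fixed before analysis. If all sessions enter, the planned model gives a valid standard error only under equal correlation of all of a patient's readings, or if the two departures happen to offset. The protocol's own sub-hypothesis on intellectual disability argues against equal correlation. Over the assumed components, type I error runs from about 0% (effect SD 0.3, session SD 1.0) through 13% (0.5, 0.5) to 27% (0.5, session SD 0, an extreme case). The net direction cannot be known from the documents.

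The missing Time × Block term is a separate and modest issue: a bias of 0.04 for an assumed drop of 0.25 at 22 versus 16, and none with equal groups.

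The pre-post paired t-tests are not touched, and a true VR-standard difference of 0.5 is detected either way. What suffers is the coverage of the interval and any conclusion about differences of roughly 0.1 to 0.3. The variance components, the drop in block 2, the group split and the reading of 0.83 and 0.74 as uncorrelated single-session change SDs are all assumptions.

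**What to change.** In Section 16.2:

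1. State that all sessions enter the VR-versus-standard comparison.
2. Take post minus pre for each session as the outcome, and say that it is used here in place of the section's ratio. It is the quantity that Time × Treatment already estimates.
3. Fit a mixed model to this change with fixed treatment, block, group and session number, and random participant and participant-by-treatment effects. If the raw readings are kept instead, add block, Time × Block, a session-within-participant intercept, and participant-level random effects for time, treatment and time-by-treatment. A block main effect alone does not remove the bias.
4. Name a period-adjusted crossover t-test on each patient's mean change per block as the check, and as the fallback if the model does not converge.

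The cost is a few lines of text and no new data. The interval will be wider if patients differ in response. The patient-mean analysis uses only patients with sessions in both blocks, which matters with 30% expected dropout and is why the mixed model comes first.

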### 23.2. Compensation for study participants

Er wordt geen vergoeding gegeven aan de deelnemers. Het voordeel voor de deelnemers is dat zij gratis 20 relaxatiesessies aangeboden krijgen door deel te nemen aan de studie.

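### The test labelled carry-over stays inside one block, so it cannot see lasting carry-over or tell fading carry-over from habituation; the crossover model also lacks Period and Time × Period terms

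*Combined protocol and SAP*

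**What the plan says.** Section 13.1 sets out the design: "The study consists of two blocks of 10 sessions: one block with VR and one without". Section 16.2 repeats the block length ("each block consisting of 10 sessions"), and section 23.2 counts the total as "gratis 20 relaxatiesessies" (20 free relaxation sessions). No washout between blocks is stated.

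Section 16.2 says that carry-over "will be examined by comparing VAS scores and physiological parameters between session 1, session 5, and session 10 using paired t-tests", with two pairs: S1 against S5 and S5 against S10. It does not say whether pre, post or change scores are compared, in which block, or whether the two sequences are pooled.

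The mixed model in section 16.2 contains Time (pre versus post within a session), Treatment, Group and Time × Treatment, with a random participant intercept. Time × Treatment is named as the main parameter. There is no Period, Time × Period, Time × Group or session-number term.

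Two hypotheses bear on this. Hypothesis 3 states that "VRelax will also reduce chronic stress through a cumulative effect". Hypothesis 4 expects that "as the number of sessions increases, habituation or boredom may occur for both standard and VR relaxation", to be seen as a "decreasing difference between pre- and post-VAS scores per individual over time". Section 7.1 asks "Is there any habituation", but section 16.2 lists no analysis under that name.

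**The concern.** Carry-over in a two-period crossover is what the first treatment leaves behind in the second period. Detecting it needs a comparison between sequences, or at least one that involves both blocks. The planned pairs do neither. What they measure is change with session number inside a block, which is how Hypothesis 4 describes habituation.

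Two wrong statements could follow in the report. A non-significant result could be given as absence of carry-over when a lasting one is present. Ordinary habituation could be given as carry-over. The plan itself makes a lasting effect plausible, since it expects VRelax to act cumulatively and states no washout.

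Separately, the model does not adjust the pre-post change for block. Every session has both a pre and a post score, so Group as a main effect shifts both equally and leaves Time × Treatment unchanged.

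**Working it through.** **Inputs.** From the documents: two blocks of 10 sessions (13.1), SDs 0.83 and 0.74, difference 0.5, N = 54, dropout 30% (10.1, 16.1). The documents do not say whether the SDs describe participants or single sessions. Assumed: the sizes of carry-over, habituation and period effects, the intraclass correlation (ICC), and a 27/27 start (13.5 gives no ratio).

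**The plan's N.** SD of the difference at zero correlation = √(0.83² + 0.74²) = 1.112. A two-sided paired t-test at 80% power needs 41, and 41 × 1.3 = 53.3, rounded up to 54. The point does not depend on this N. The checks use 54 × 0.70 = 37.8, or 38 participants.

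**Step 1: algebra.** Let a carry-over c be constant through block 2. It adds c to S1, S5 and S10, so S1 − S5 and S5 − S10 each contain c − c = 0. This holds for pre, post and change scores, pooled or by sequence. If sessions were numbered 1 to 20, sessions 1, 5 and 10 would all precede the switch.

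**Step 2: what triggers the tests.** Simulation on the pre-post change (one reading of the plan), n = 38, session SD 0.83, ICC 0.3, 6,000 runs per setting:

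| Scenario | S1 vs S5 | S5 vs S10 |
|---|---|---|
| Nothing present | 4.9% | 4.8% |
| Lasting carry-over 0.5 in the VR-first half | 5.3% | 5.5% |
| Carry-over 0.5, halving each session, same half | 28.2% | 4.9% |
| Habituation 0.05 per session, no carry-over | 22.7% | 34.0% |

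Hand check: the SD of a paired difference is 0.83 × √(2 × 0.7) = 0.982, with standard error 0.982/√38 = 0.159. Habituation gives mean differences of 4 × 0.05 = 0.20 and 5 × 0.05 = 0.25. Halving carry-over gives (0.5 − 0.5/16)/2 = 0.234 for S1 vs S5, close to the habituation value.

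Over ICC 0.1 to 0.7, lasting carry-over stays at about 5% and halving carry-over ranges from 24% to 53% (S1 vs S5). Over the same ICCs and slope SD 0 or 0.1, habituation ranges from 17% to 47% and from 23% to 64%.

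A second simulation used other variances (between-person SD 0.6, person-by-block 0.3, session 0.5) and tested block 2 of 19 VR-first participants. Lasting carry-over of 0.5 was flagged 5.0% and 5.3% of the time, against 5.4% and 4.9% with none.

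**Step 3: effect on the primary parameter.** With complete sequences, carry-over in the change raises half of the standard sessions: 0.50 − 0.5/2 = 0.25. Adding Time × Period does not help: the value is still 0.25 with complete sequences. When 22 VR-first and 16 standard-first participants complete block 2 it is 0.276 without the term and 0.297 with it; at 24/14, 0.265 and 0.302.

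**Step 4: missing Time × Period.** For a period effect p, with nA and nB the VR-first and standard-first participants completing block 2:

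- all available sessions: 0.5 + p × [nB/(27 + nB) − nA/(27 + nA)]
- completers only: 0.5 + p × (nB − nA)/38

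| nA/nB | Data | p = −0.1 | p = −0.25 | p = −0.5 |
|---|---|---|---|---|
| 22/16 | all sessions | 0.508 | 0.519 | 0.538 |
| 24/14 | all sessions | 0.513 | 0.532 | 0.565 |
| 22/16 | completers | 0.516 | 0.539 | 0.579 |
| 24/14 | completers | 0.526 | 0.566 | 0.632 |

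The shift reverses if standard-first is the larger group. A random-intercept fit to low-noise 22/16 data (all sessions, p = −0.5) gave 0.540 with or without Group and 0.502 with Time × Period. A split of 22/16 or worse has probability 13.5% under fixed 27/27 allocation and 42% under simple randomisation; for 24/14 or worse, 0.6% and 14%.

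With equal, complete sequences there is no bias. On a simplified participant-level paired test (n = 38, r = 0; not the planned model), p = 0.5 lowers power from 77% to 69% if the SDs are participant-level, or from 99% to 95% if session-level with ICC 0.3.

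**The case against.** - **Hypothesis 3 concerns chronic stress on the PSS, while the primary parameter is a within-session change.** This stands in part. A carried-over fall in stress that moves pre and post scores equally drops out of Time × Treatment. Only carry-over in the size of the change biases it, and the documents do not predict that. The sign is also open: −0.5 would give 0.75 instead of 0.25. Hypothesis 3 makes a lasting effect plausible; it does not establish bias. The test is still blind to either kind when it is constant.
- **Pre-session scores drifting within the VR block would show an accumulating effect.** True, but that bears on persistence under VR, not on what is carried into the other block.
- **Block 1 contains habituation without carry-over, so contrasting block-1 and block-2 trends could partly separate the two.** Also true, as could the pattern across the two pairs. The plan specifies neither, and lasting carry-over would still be missed.
- **This may be the habituation analysis under the wrong name, and it does not gate anything.** Quite possibly. Then the plan has no carry-over analysis at all, and the harm is a wrong statement in the report, not a changed primary estimate.
- **The period issue is small.** Agreed; it is secondary.

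**Conclusion.** The concern holds. The blindness to constant carry-over follows from the session numbering and needs no assumed effect size. The confusion of fading carry-over with habituation follows from the plan's pairs and from the absence of any contrast between blocks or sequences. The percentages are illustrations resting on assumed effects, ICCs and an SD level the documents leave open; the pattern was the same under two sets of variance assumptions.

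The consequence is a possible wrong claim about carry-over in either direction. If carry-over in the change exists, the primary estimate is biased by about minus half its size, and the planned test gives no warning when that carry-over is constant. The absent period terms matter less: no bias with balance, and shifts of about 0.01 to 0.06 points with all sessions, or 0.02 to 0.13 with completers only, in the cases examined. This should be corrected in the analysis plan.

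**What to change.** 1. Add Period (block 1 versus 2) and Time × Period to the mixed model.
2. Relabel the S1/S5/S10 comparison as habituation. Analyse the pre-post change with a Time × session-number term by treatment over all 10 sessions, with participant-level slopes. In the simulation above (ICC 0.3), a slope over all 10 sessions detects 0.05 per session with power 97.5%, or 66% with slope SD 0.1.
3. Report Time × Group, on participant-level mean changes, with its confidence interval, and a block-1-only comparison of VR with standard. Both are sensitivity analyses and must not gate the primary analysis.
4. State in advance that a non-significant Time × Group result does not show that carry-over is absent, and that Time × Period does not remove carry-over bias.

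The cost is plan wording and two fixed effects in the primary model; block, session number and sequence are known for every session.

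These changes check for carry-over but do not correct it, and Time × Group cannot be separated from a chance difference between sequences. With 19 per sequence, its power for a carry-over of 0.5 is about 20–27% (participant-level SDs) or 44–60% (session-level, ICC 0.3), with a 95% interval of about ±0.45 to ±0.9 points. For an effect of 0.5, the block-1-only comparison has about 48% (participant-level) to 84–88% (session-level) power with 19 per group, and 63% to 95–97% with 27.
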